8.3.2 Other Secondary Endpoint(s)

None.

8.4 Safety Endpoint(s)

8.4.1 Primary Safety Endpoint(s)

Safety analyses will include tabulations of the incidence (number and percent of subjects) of treatment-emergent adverse events (TEAEs) and procedure-related AEs by MedDRA system organ class (SOC) and preferred term (PT). This will be repeated for serious adverse events, for adverse events leading to study withdrawal and for adverse events at least possibly related to study procedures. This will be performed on the safety population.

8.4.2 Secondary Safety Endpoint(s)

None.

8.5 Demographics and Baseline Characteristics

Demographic profiles including age, gender, race, ethnicity, height, weight and BMI will be summarized for all Safety evaluable subjects. Descriptive statistics (n, mean, median, standard deviation, minimum and maximum) will be provided for each quantitative variable, and frequencies and percentages will be provided for each categorical variable.

8.6 Interim Analysis

This study will utilize an adaptive design that allows one interim sample size re-calculation after a minimum of 75 subjects have been enrolled and followed. The pre-specified maximum allowable adjusted sample size following re-estimation will be 300 enrolled, or two times the initial planned sample size of 150 enrolled. The re-estimation of sample size will be conducted by an independent biostatistician following a pre-specified plan using the method of by Mehta and Pocock (2011).¹ Specifically, at the interim stage the conditional power (CP) for obtaining a significant beneficial effect of DEFINITY® over unenhanced imaging with respect to the primary endpoint will be calculated for each blinded reader, using the protocol-specified planned sample size of 150 enrolled subjects (approximately 143 evaluable subjects assuming 5% premature withdrawal). This conditional power will be calculated under the assumption that the interim estimate of DEFINITY® -unenhanced difference is the true population difference. Specifically, the calculation of conditional power will be as follows:

Let μ_D be the true mean of the absolute value of the LVEF differences between the DEFINITY®-enhanced echo LVEF and the CMR LVEF, and let μ_U be the true mean of the absolute value of the LVEF differences between the unenhanced echo LVEF and the CMR LVEF. After 75 patients are enrolled and followed (which should lead to approximately 71 evaluable patients), an unblinded interim analysis will be conducted to determine whether sample size should be increased to maintain adequate conditional power of up to 90% for each reader. Conditional Power (CP) for rejecting the null hypothesis in favor of DEFINITY® by the planned final sample size of 143 evaluable patients is calculated as follows for each reader:

$$CP = P \left(Z > \frac{c_2 \sqrt{i_2} - t_1 \sqrt{i_1} - (I_2 - I_1)\Delta}{\sqrt{i_2 - i_1}} \right)$$

where

- a. Z is a random standard normal variate
- b. c_2 is the *t*-critical value to be used in the final analysis = 1.97681 (one-sided 0.025 level of significance; , with 142 df assuming the final evaluable sample size is 143, which is the number of evaluable subjects expected for the final analysis with 150 enrolled subjects with 5% premature withdrawal)

- c. Δ is the assumption of the true difference “ μ_U minus μ_D ” where μ_D is the mean of the absolute value of the differences between the DEFINITY®-enhanced echo LVEF and the CMR LVEF, and μ_U is the mean of the absolute value of the differences between the unenhanced echo LVEF and the CMR LVEF; Δ will be set to the value observed at the interim (the calculation of Δ is described below; it is not correct to calculate it as the interim point estimate of μ_U minus the interim point estimate of μ_D).
- d. I_1 is the observed “information” at the interim analysis based on the interim observed standard deviation of μ_D minus μ_E ; its calculation is described below.
- e. I_2 is the anticipated “information” at the final analysis; its calculation is described below.
- f. t_1 is the interim paired t-statistic testing the null hypothesis, calculated from the data observed at the interim

Further information on the above parameters is as follows:

Assuming the Definity-CMR raw LVEF difference (not absolute value) is normally distributed with mean μ and sd σ , then its absolute value, D , follows the *folded normal* distribution with true mean and sd as follows:

$$\mu_D = \sqrt{\frac{2}{\pi} \sigma e^{-\frac{\mu^2}{\sigma^2}} + \mu \left[1 - 2\Phi\left(-\frac{\mu}{\sigma}\right) \right]} \quad \sigma_D = \sqrt{\mu^2 + \sigma^2 - \mu_D^2}$$

where ϕ is the standard normal cumulative distribution function. A similar algorithm can be applied to the unenhanced-CMR LVEF raw difference and its absolute value U to determine μ_U and σ_U . In the above CP formula, Δ will be set to the estimate of $\mu_D - \mu_U$, where the estimates of μ_U and μ_D are each calculated from the above equation using point estimates of the relevant μ and σ . The standard deviation of the difference between the absolute value of D minus the absolute value of U is

$$\sqrt{\sigma_D^2 + \sigma_U^2 - 2 * Cov(D, U)} \text{ where } 2 * Cov(D, U) = \rho * \sigma_D * \sigma_U$$

where ρ is the correlation between D and U . This standard will be used in the calculation of the “information”, as further described below.

So, in the CP formula for this example,

- a. Δ will be set to the estimate of $\mu_D - \mu_U$
- b. $I_1 = \frac{1}{s^2/n_1}$ where s = the interim estimate of the above standard deviation between the absolute values D and U
- c. $I_2 = \frac{1}{s^2/n_2}$ where s - the interim estimate of the above standard deviation between the absolute values D and U and n_2 is the planned final sample size = 143.

- The study will not be stopped for overwhelming efficacy or futility at this interim stage. Instead, based on Table 1 of Mehta and Pocock (2011),¹ the following algorithm will be carried out: (1) if the CP $\leq 36\%$ for at least two of the three blinded readers based on the final sample size, the study will continue to its original planned sample size of 150 enrolled subjects; otherwise (2) if the CP $\geq 90\%$ for at least two of the three blinded readers based on the final sample size, the study will continue to its original planned sample size of 150 enrolled subjects; (3) if $36\% < CP < 90\%$ (the Mehta and Pocock “promising zone”) for at least two of the three readers based on the final sample size, then the sample size will be increased so that the CP is at least 90% for every reader whose CP fell in the promising zone. However, if there is a reader who does not fall in the promising zone, then that reader’s primary results will be based only on the patients enrolled under the original protocol-specified sample size. Further, for every reader for whom the sample size is increased, that reader’s results will only be based on the first X images, where X is the number of images that yielded CP of 90%. The sample size may be increased up to 300 enrolled subjects (twice the protocol-planned sample size) for a given reader in order to obtain 90% CP. If for a given reader that falls into the promising zone, the maximum increase to 300 enrolled subjects still does not yield 90% CP, the sample size may still be increased to 300 for this reader to maximize conditional power, at the discretion of the independent statistician). If (1), (2), and (3) above are not satisfied, the study will continue to its original planned sample size of 150 enrolled subjects. This approach to sample size increase does not inflate the overall Type I error for a given reader.

The sponsor and investigators will remain blinded to the interim results for the duration of the ongoing study. After the interim analysis is carried out, the recommendation made to the sponsor will only be to keep sample size as is or to increase enrolled sample size to a given value; the reason for the recommendation will not be given to the sponsor.

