This analysis plan is based on the protocol dated 15-Aug-2018, amendment 3, and the original SAP, dated 06-Oct-2018, approved by the FDA along with the protocol. As Syneos Health was commissioned to perform the statistical analysis, they were also asked to write a SAP following enrollment in the study.

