2.2. Timings of Analyses

The primary analysis of safety and efficacy will take place after all subjects complete the final study visit, or terminate early from the study, and the database has been locked.

An interim analysis to evaluate sample size assumptions will be conducted when a minimum of 75 subjects have been enrolled and imaged. An unblinded team from Syneos Health biostatistics will perform the analyses as described in Section 10.0 of this SAP to maintain the blinding of the study.

This document is confidential.

3. Study Objectives

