Let μ_D be the true mean of the absolute value of the differences between the DEFINITY®-enhanced echo LVEF and the CMR LVEF, and let μ_U be the true mean of the absolute value of the differences between the unenhanced echo LVEF and the CMR LVEF. After a minimum of 75 subjects are enrolled and followed (which should lead to approximately 71 evaluable subjects), an unblinded interim analysis will be conducted to determine whether sample size should be increased to maintain adequate conditional power of up to 90% for each reader. Conditional Power (CP) for rejecting the null hypothesis in favor of DEFINITY® by the planned final sample size of 143 evaluable subjects is calculated as follows for each reader:

$$CP = P \left(Z > \frac{c_2 \sqrt{I_2} - t_1 \sqrt{I_1} - (I_2 - I_1)\Delta}{\sqrt{I_2 - I_1}} \right)$$

where,

- a. Z is a random standard normal variate
- b. c_2 is the t -critical value to be used in the final analysis = 1.97681 (one-sided 0.025 level of significance; with 142 degrees of freedom assuming the final evaluable sample size is 143, which is the number of evaluable subjects expected for the final analysis with 150 enrolled subjects with 5% premature withdrawal).
- c. Δ is the assumption of the true difference “ μ_U minus μ_D ” where μ_D is the mean of the absolute value of the differences between the DEFINITY®-enhanced echo LVEF and the CMR LVEF, and μ_U is the mean of the absolute value of the differences between the unenhanced echo LVEF and the CMR LVEF; Δ will be set to the interim sample's point estimate of μ_U minus μ_D ; i.e., Δ will be set to $\bar{x}_U - \bar{x}_D$, where \bar{x}_U and \bar{x}_D are the sample mean point estimates of μ_U and μ_D , respectively.
- d. I_1 is the observed “information” at the interim analysis; specifically, $I_1 = \frac{1}{s^2/n_1}$ where s = the interim sample point estimate of the standard deviation of the difference between the unenhanced and DEFINITY® echo's “absolute value of the difference versus CMR” and n_1 is the interim sample size.
- e. I_2 is the anticipated “information” at the final analysis; specifically, $I_2 = \frac{1}{s^2/n_2}$ where s is as defined in item 'd' directly above and n_2 is the planned final evaluable sample size = 143.

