11.1. Changes from Analysis Planned in Protocol

There have been no changes in analyses from those defined in the protocol.

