11.2. Changes from Analysis Planned in FDA Approved Statistical Analysis Plan (06Oct2018)

The variable 'Age' has been amended from being a derived value to being a reported value. No date of birth is collected for subjects in this study.

In section 3.6, a section was added to clarify that the study statistical team will remain blinded to the reader and CMR reported results until all subjects complete the final study, or terminate early from the study, and the database has been locked. A separate unblinded statistical team will create the unblinded results to be reviewed during the IA. The reason for this amended text is to ensure the study statistical team will also remain blinded to the IA study results along with the sponsor and investigators.

In section 8, it is noted that approximately 10% of the imaging scans will be re-read by each reader. Unless otherwise specified, the original read is what will be used for all reporting and statistical analyses. Further, in section 8.2.2, a separate ICC analysis was added to assess intra-reader variability. Any additional information regarding the re-reading of scans can be found in the Imaging Charter for this study.

In the vital signs table, section 9.5, the following updates have been made:

- For Heart Rate, the phrases 'and $\geq 25\%$ decrease (increase) from baseline' were removed
- For Systolic blood pressure, the phrases '(entry is < 160 mmHg' and 'decrease from baseline > 30 mmHg' were removed
- For Diastolic blood pressure, the phrases '(entry is < 90 mmHg)' and 'change from baseline of 20 mmHg (increase or decrease)' were removed; and a greater than sign was added in front of the Potentially Clinically Significant value of 110 mmHg as it was missing in the previous FDA approved SAP

Since the vital signs are only collected once, at the screening/baseline visit, there will be no way to determine increases/decreases from baseline.

In section 10 (interim analysis), the two bullets to clarify how to proceed with the study in cases of $CP \leq 36\%$ or $CP \geq 90\%$ have been added for clarification, along with additional text regarding how to evaluate the final study results.

This document is confidential.

12. Reference List

1. Hamer RM. INTRACC.SAS Macro to Calculate Reliabilities for Intraclass Correlations [Internet]. SAS Institute;1990 [cited 15 January 2018]. Available from <https://github.com/friendly/SAS-macros/blob/master/intracc.sas>.

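### Protocol 8.6 and SAP 10 prescribe different conditional-power inputs for the sample-size decision, SAP 11.1 declares no change, and 8.6 contradicts itself on the sign of Δ

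*Protocol*

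**What the plan says.** **Protocol 8.6.** Item c defines Δ as μ_U minus μ_D, the mean absolute error against CMR for unenhanced echo minus that for DEFINITY. It adds that "it is not correct to calculate it as the interim point estimate of" μ_U minus the corresponding estimate of μ_D. Instead, each mean is obtained by putting the mean and SD of the raw (signed) differences from CMR into the folded-normal formula. The SD that enters I1 and I2 is built from σ_D, σ_U and the correlation ρ. The text below item c then says twice, once in the paragraph under the folded-normal formula and once in the short list after it, that Δ is the estimate of μ_D − μ_U.

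**SAP 10.** Item c sets Δ to x̄_U − x̄_D, which "are the sample mean point estimates of" the two means. Item d takes s as "the interim sample point estimate of the standard deviation of the difference between the unenhanced and DEFINITY" absolute errors against CMR. Item f derives t1 from the same sample mean and SD.

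**Status of the two texts.** SAP 2.2 says the unblinded team "will perform the analyses as described in Section 10.0 of this SAP". SAP 2 bases the plan on protocol amendment 3 and on "the original SAP, dated 06-Oct-2018, approved by the FDA along with the protocol". SAP 11.1 states: "There have been no changes in analyses from those defined in the protocol". SAP 11.2 lists changes since the October 2018 SAP. Its entry for this section begins "In section 10 (interim analysis), the two bullets to clarify how to proceed with the study in cases of" low or high CP and also mentions text on evaluating the final results. It names neither Δ nor s.

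**The concern.** One document forbids the calculation that the other prescribes, so the SAP text cannot be read as filling in detail. The SAP's statement that nothing changed is untrue for both Δ and s.

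The re-estimation is meant to follow a pre-specified plan run by an independent statistician. With two incompatible sets of inputs on file, the choice between them could be made, or questioned, after unblinded data have been seen. Protocol 9.8 provides no data monitoring committee, and both documents withhold the reason for the recommendation from the sponsor, so a wrong input would not show in the recommendation itself.

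The sign is a separate fault, internal to the protocol. The CP formula gives the chance of rejecting in favour of DEFINITY, so it needs Δ positive when DEFINITY is more accurate. The twice-repeated assignment makes it negative.

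**Working it through.** **1. The plan's own figures reproduce.** The inputs are a difference of 2.75, SD 10, two-sided 0.05, and 150 enrolled or 143 evaluable (Protocol 8.2.1 and 8.6). The noncentral t with parameter 0.275 × √143 gives power 90.4%, against a stated 90%. The 0.975 t quantile on 142 df is 1.97681, as stated. The design calculation is not in question.

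**2. The CP formula with aligned signs.** CP = P(Z > [c2√I2 − t1√I1 − (I2 − I1)Δ] / √(I2 − I1)), with I = n/s², n1 = 71 and n2 = 143. Take s = 10, so I1 = 0.71, I2 = 1.43, and c2√I2 = 1.97681 × 1.1958 = 2.364. At an observed difference of 2.75:

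- t1√I1 = 0.71 × 2.75 = 1.9525
- (I2 − I1)Δ = 0.72 × 2.75 = 1.98
- (2.364 − 1.9525 − 1.98)/0.8485 = −1.849, so CP = 96.8%

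**3. The sign taken literally.** With Δ = −2.75 and t1 still positive, (2.364 − 1.9525 + 1.98)/0.8485 = 2.818, so CP = 0.24%. If t1 is reversed as well, CP is effectively zero.

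| Observed difference (s = 10) | CP, Δ = μ_U − μ_D | CP, Δ = μ_D − μ_U, t1 positive |
|---|---|---|
| 1.5 | 39.8% | 0.25% |
| 2.0 | 72.1% | 0.25% |
| 2.25 | 84.3% | 0.25% |
| 2.75 | 96.8% | 0.24% |

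With the correct sign, the 36–90% zone covers observed differences of about 1.44 to 2.41. With the reversed sign, no reader showing a benefit could enter it. This is what the words say, not what I expect anyone would run.

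**4. The estimator conflict, with the sign aligned.** Both versions use the sample paired t as t1.

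- SAP version: Δ is the sample mean difference and s the sample SD of the paired difference.
- Protocol version: for each modality, with m and σ the sample mean and SD of the raw differences, the folded mean is σ√(2/π)·exp(−m²/2σ²) + m[1 − 2Φ(−m/σ)] and the folded variance is m² + σ² − (folded mean)². Then s = √(σ_D² + σ_U² − 2ρσ_Dσ_U), with ρ the sample correlation of the absolute errors. I used these standard formulas because the printed equations may be damaged in extraction.

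The documents give no bias, SD or correlation for the raw errors, so all of these are assumed. The ten normal scenarios, written as (DEFINITY mean, SD; unenhanced mean, SD; correlation), are: (0,8; 0,11; 0.2), (−3,8; −6,11; 0.7), (0,10; 0,13; 0.5), (−2,10; −5,13; 0.5), (−3,14; −6,17.5; 0.2), (0,14; 0,17.5; 0.7), (−1,9; −4,12; 0.4), (−3,12; −6,14; 0.6), (0,8; −6,11; 0.5), (−1,12; −3,15; 0.3). Each was run with between-reader correlation 0.3, 0.6 and 0.9, using 20,000 interims of 71 subjects and three readers.

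The decision compared is the same in both documents: increase if at least two of three readers have CP between 36% and 90%.

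| Result | Range over scenarios |
|---|---|
| Reader placed in a different CP zone | 0.9–11.9% |
| Increase/no-increase decision differs | 0.1–13.3% |
| Only the SAP rule increases | 0.1–5.5% |
| Only the protocol rule increases | 0.0–8.0% |

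The lowest disagreement is in (−3,8; −6,11; 0.7), where CP is nearly always above 90%. The highest is in (−3,12; −6,14; 0.6).

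The scenario nearest the design values is (0,14; 0,17.5; 0.7). Its true difference is 0.798 × 3.5 = 2.79. The folded SDs are 14 × 0.603 = 8.44 and 17.5 × 0.603 = 10.55. The correlation of the absolute errors is 0.637 × (√0.51 + 0.7 × arcsin 0.7 − 1)/0.363 = 0.45. The SD of the paired difference is therefore √(71.2 + 111.3 − 80.1) = 10.1. Disagreement there is about 11% per reader and 10.8–11.9% for the decision.

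**5. Conditional note on covariance.** As extracted, Protocol 8.6 equates 2Cov(D,U) with ρσ_Dσ_U, whereas the identity is 2ρσ_Dσ_U. If the extraction is faithful, s is too large when ρ is positive. With equal σ and assumed ρ of 0.2 to 0.4, a CP of 39.8% becomes 37.0% to 33.4%, and 92.3% becomes 90.4% to 87.3%. SAP 10 does not use this formula.

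**The case against.** The operative rule is arguably settled. Protocol 8.1.1 leaves further detail to the SAP, SAP 2.2 sends the unblinded team to SAP 10, and SAP 10 has one sign, one Δ, one s and a matching t1. On that view the fault is one of traceability. This stands, and it is why the point is not graded higher. It does not make SAP 11.1 true, nor does it remove the protocol's explicit rejection of the SAP method.

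The sign reversal looks like a drafting slip, since item c and the CP formula both require μ_U − μ_D. I agree, and I do not count the 0.24% as an expected outcome.

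The simulated percentages rest on assumed error distributions. Mean CP differs between the rules by only 0.2–1.6 points. About 58–90% of zone disagreements fall at the 90% cut-off, where an increase is often modest: with s = 10, an observed difference of 2.25 needs 174 evaluable, or 174/0.95 ≈ 184 enrolled. That is fair. Even so, where the zones do differ the median CP gap is about 9–12 points, and the disagreement changes the recommendation.

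The folded-normal plug-in is a legitimate estimator if the raw errors are normal, so the documents themselves require only that one rule be chosen. The reason to prefer the SAP version is that it matches t1 and the final paired t-test and needs no normality assumption.

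The silence of SAP 11.2 suggests that the sample estimator was already in the October 2018 SAP. That document is not available here, so this remains an inference.

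**Conclusion.** The concern holds and should be fixed. The estimator conflict, the untrue statement in SAP 11.1 and the sign contradiction in Protocol 8.6 all rest on running text and are certain. The size of the estimator effect depends on assumed normal errors: opposite increase/no-increase decisions in 0.1–13.3% of simulated interims, and about 11–12% near the design values, in both directions. The covariance point is conditional on the extracted equation and has no effect under SAP 10. The adaptation is workable if SAP 10 is followed. The final test statistic and the stated 90% power are untouched.

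**What to change.** Before the interim is run, bring Protocol 8.6 into line with SAP 10:

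- Define Δ as x̄_U − x̄_D, s as the sample SD of the paired difference, and t1 with the same sign.
- Delete the sentence rejecting that estimate, both μ_D − μ_U assignments, and the covariance formula along with the folded-normal derivation it serves.
- Replace the SAP 11.1 statement with an entry recording that Δ and s differ from protocol amendment 3.

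The cost is a protocol clarification and one SAP entry, with no change to data collection, the final test or the 150-subject calculation. SAP 2 says this plan was requested after enrolment in the study, so the documents do not show whether the interim is still ahead. If it has already been run, make the SAP 11.1 entry and document which inputs were used.

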8.2 Efficacy Endpoint(s)

8.2.1 Primary Efficacy Endpoint

The primary analysis is to demonstrate an improvement in LVEF accuracy from unenhanced imaging to imaging with DEFINITY® contrast enhancement using CMR as the truth standard. For each patient, the absolute value of the difference of DEFINITY® LVEF minus CMR LVEF will be calculated. Similarly, the absolute value of the difference of unenhanced imaging LVEF minus CMR LVEF will be calculated for each patient. The primary analysis is to assess the significance of the difference between DEFINITY® and unenhanced echo with respect to the mean “absolute value of the difference vs. CMR”. These means will be compared with a paired t-test at a two-sided 0.05 level of significance. Specifically, the null and alternative hypotheses are:

$$H_0: \mu_D = \mu_U \text{ vs. } H_1: \mu_D \neq \mu_U$$

where μ_D and μ_U are the mean of the DEFINITY® and unenhanced echo absolute value of the difference vs. CMRs, respectively. A sample of size 150 enrolled subjects has 90% power to reject the null hypothesis in favor of the alternative if the true difference $\mu_D - \mu_U$ is at least 2.75 (in favor of DEFINITY®) with a standard deviation of 10 or less and allows for approximately 5% premature withdrawal.

The analyses will be conducted separately for each of the three blinded readers of the DEFINITY® enhanced and unenhanced images; the criterion for success is that the null hypothesis is rejected in favor of DEFINITY® for at least 2 of the 3 blinded readers. CMR LVEF is interpreted by a single reader; this is the CMR LVEF that will be used as the comparator for each of the three blinded readers.

The primary analysis will be performed on mITT subjects with non-missing LVEF for DEFINITY®, unenhanced echocardiography, and the reference standard. A supportive analysis will be run where a missing echocardiography or CMR LVEF is multiply imputed using the fully conditional specification (FCS) multiple regression, as outlined below and as will be further detailed in the Statistical Analysis Plan.

The following are additional analyses to be carried out separately for each blinded reader to achieve the primary objective:

Bias is the mean of the actual (not absolute value) per-subject differences between the imaged LVEF and CMR LVEF. The bias, the two-sided 95% confidence interval of the bias,

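### As printed, Protocol 8.6 omits a factor of 2 in the folded-normal exponent; it matters to the interim only if the protocol's method is used rather than SAP 10's, a conflict SAP 11.1 does not declare

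*Protocol*

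**What the plan says.** Protocol 8.6 assumes that the raw echo-minus-CMR difference is normal with mean μ and SD σ, so that its absolute value is folded normal. It then gives the mean of that absolute value with an exponential term that reads "\sigma e^{-\frac{\mu^2}{\sigma^2" (a fragment of the machine-read equation). The folded SD is the square root of μ² + σ² minus the square of that mean. The estimates of μ_U and μ_D "are each calculated from the above equation using point estimates of the relevant" μ and σ. They set Δ and, through the folded SDs, the information terms I₁ and I₂ in the conditional-power (CP) formula. The same section says that taking Δ as the difference of the two interim point estimates is incorrect.

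SAP 10 does what the protocol rules out. Δ is the difference of the interim sample means of the absolute errors, s is the sample SD of the paired difference, and no folded normal appears. SAP 2.2 tells the unblinded team to work from SAP 10. SAP 11.1 states: "There have been no changes in analyses from those defined in the protocol".

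**The concern.** The printed exponent is not that of the distribution the protocol names. The resulting mean feeds Δ directly and feeds s through the folded SD, so one slip alters both inputs to CP. The interim rule sorts each reader's CP into at most 36%, between 36% and 90%, or at least 90%, and may raise enrolment from 150 to as many as 300. If contrast works mainly by removing bias, the printed form hides part of that gain. A reader with adequate CP could be placed in the promising zone, or a promising reader in the unfavourable one.

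With two opposite instructions for Δ and s in force and no declared change, it is also unclear which calculation is the pre-specified one.

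**Working it through.** **The plan's own figures.** Protocol 8.2.1: "These means will be compared with a paired t-test at a two-sided 0.05 level of significance"; "A sample of size 150 enrolled subjects has 90% power to reject the null hypothesis" when the difference "is at least 2.75 (in favor of DEFINITY®) with a standard deviation of 10 or less", and the number "allows for approximately 5% premature withdrawal". 150 × 0.95 = 142.5, taken as 143. The noncentrality is (2.75/10) × √143 = 3.29, and the noncentral t with 142 df gives 90.4% power. Protocol 8.6 gives the "critical value to be used in the final analysis = 1.97681"; the 0.975 quantile of t with 142 df is 1.97681. Both figures reproduce, and neither uses the folded-normal equation.

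**The folded-normal mean.** For X ~ N(μ, σ):

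E|X| = σ√(2/π)·exp(−μ²/(2σ²)) + μ[1 − 2Φ(−μ/σ)].

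As printed, the radical covers the whole right-hand side, which is dimensionally inconsistent (2.62 at μ = 5, σ = 10). I place it over 2/π only and test the exponent alone.

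- μ = 5, σ = 10: standard 7.979 × 0.8825 + 1.915 = 8.96; printed 7.979 × 0.7788 + 1.915 = 8.13. Simulation gives 8.96.
- μ = σ = 10: standard 11.67, printed 9.76. A mean absolute value cannot be smaller than the absolute value of the mean, here 10, so the printed form is impossible.

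In units of σ:

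| abs(μ)/σ | Mean, standard | Mean, printed | Understated by | SD, standard | SD, printed |
|---|---|---|---|---|---|
| 0.25 | 0.823 | 0.799 | 2.9% | 0.621 | 0.651 |
| 0.5 | 0.896 | 0.813 | 9.2% | 0.669 | 0.768 |
| 0.75 | 1.012 | 0.865 | 14.6% | 0.733 | 0.903 |
| 1.0 | 1.167 | 0.976 | 16.3% | 0.799 | 1.023 |

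At μ = 0 the two forms agree.

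**Conditional power.** With I = n/s², the plan's formula becomes

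CP = P(Z > [c₂√n₂ − t₁√n₁ − (n₂ − n₁)Δ/s] / √(n₂ − n₁)),

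with n₁ = 71, n₂ = 143 and c₂ = 1.97681 from the protocol, so c₂√n₂ = 23.639. Bias, SD and the correlation ρ between the two absolute errors are not in the documents; the values below are assumptions. I take Δ = μ_U − μ_D and the covariance as ρσ_Dσ_U, doubled in the variance. t₁ is the observed paired t-statistic, which the equation does not touch; I set it to its expected value Δ√n₁/s under the correct moments.

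Example (a), ρ = 0.3: unenhanced bias −6, SD 9; enhanced bias −3, SD 8; t₁ = 2.312.
- Standard: Δ = 1.893, s = 6.901. (23.639 − 19.480 − 19.754)/8.485 = −1.838, CP 96.7%.
- Printed: Δ = 1.152, s = 8.079. (23.639 − 19.480 − 10.263)/8.485 = −0.719, CP 76.4%.

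Example (b), ρ = 0.3: unenhanced −5, SD 9; enhanced −2, SD 8.5; t₁ = 1.605.
- Standard: Δ = 1.293, s = 6.785. (23.639 − 13.526 − 13.717)/8.485 = −0.425, CP 66.4%.
- Printed: Δ = 0.593, s = 7.617. (23.639 − 13.526 − 5.602)/8.485 = 0.532, CP 29.7%.

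Varying the assumed correlation:

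| ρ | (a) standard → printed | (b) standard → printed |
|---|---|---|
| 0.3 | 97% → 76%, crosses 90% | 66% → 30%, crosses 36% |
| 0.5 | 99.6% → 91%, same zone | 84% → 45%, same zone |
| 0.6 | 99.9% → 96%, same zone | 92% → 57%, crosses 90% |

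**Cases with little or no effect** (ρ = 0.3).
- Bias −4 for both, SD 10 unenhanced and 8 enhanced: Δ goes from 1.44 to 1.54, CP from 75% to 72%.
- Bias −4 and SD 9 for both: Δ is 0 either way; only s changes, from 6.99 to 7.87.

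**The case against.** The strongest answer is that the interim team will not use this equation. SAP 2.2 sends it to SAP 10, which works from sample moments throughout, so the exponent has no effect on CP, zone or sample size. This stands, and it is the main limit on the point. It does not dispose of it, because the protocol expressly rejects that calculation of Δ and the SAP declares no departure.

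Second, the evidence is one small character in a machine-read equation whose radical is plainly garbled. A lost 2 in an exponent would be the same kind of damage. This also stands: the source PDF must be checked before the exponent is called a protocol error.

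Third, the same block contains other discrepancies. Δ is defined as μ_U − μ_D and later set to μ_D − μ_U, and the covariance term lacks a factor of 2. In both examples at ρ = 0.3 the sign reversal alone takes CP to about 0.2%, a larger effect than the exponent's. These are separate from the exponent; correcting them would leave it wrong.

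A reader might infer that Δ is wrong whenever echo is biased against CMR, or that the trial's sample size will be wrong. The documents support neither. Δ's errors cancel when both methods share |bias| and SD. The zone changes rest on assumed inputs. Each example is a single reader, while an increase needs at least two of three in the promising zone. The readers do share the same scans and one CMR read, so their biases may be similar, but the documents give no figures on this.

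**Conclusion.** The point holds conditionally. As the text reads, the exponent in Protocol 8.6 is wrong for the folded normal, subject to confirmation in the source PDF. Under the protocol's method, mean absolute error is understated by about 3% to 16% for |bias|/SD from 0.25 to 1, and its SD is overstated at any non-zero bias. Δ is usually distorted as well, though not always downward. A single reader's CP can then cross 36% or 90%; whether it does depends on bias, SD and correlation values that the documents do not give.

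Under SAP 10 there is no effect on the interim decision. The stated 90% power, the critical value and the final paired t-test are untouched in either case. What needs action is that protocol and SAP give opposite instructions for Δ and s, the protocol's version is mathematically wrong as printed, and SAP 11.1 says nothing changed.

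**What to change.** First check the equation in the source PDF. Then, preferably, delete the folded-normal block from Protocol 8.6, together with the statement that the sample estimate of Δ is incorrect. State that Δ and s are the interim sample mean and sample SD of the paired difference in absolute error, unenhanced minus DEFINITY, as in SAP 10. Record this in SAP 11.1.

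If the block is kept, print the mean as σ√(2/π)·exp(−μ²/(2σ²)) + μ[1 − 2Φ(−μ/σ)], with the radical over 2/π only, use the same form for both methods, and align SAP 10 with it.

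The cost is one deleted block or one corrected equation in the protocol, plus one line in SAP 11.1 (or the matching edit to SAP 10 if the block is kept). No patients and no new data are needed.
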